### **15.7.3 Clinical Laboratory Evaluations**

The analysis of laboratory parameters will be presented separated into blood parameters (hematology, serum chemistry, endocrinology, coagulation) and urine parameters (urinalysis). All data will be listed.

For hematology and serum chemistry, the laboratory values will be transformed to SI values based on SI units to make laboratory parameters comparable between different local laboratories. The relevant reference ranges supplied by each laboratory will also be transformed to SI reference ranges for each laboratory.

Descriptive summaries of actual (absolute) values and changes from baseline values will be presented for hematology and serum chemistry by treatment arm and dose level for the Safety Population.

Each abnormal value will be flagged to show whether it is a value below or above the reference range. For the assessment of laboratory variables, five categories will be used that determine the investigator's assessment of clinical relevance: 'clin. rel., above', 'non-clin. rel., above', 'within', 'non clin. rel., below', 'clin. rel., below'.

The assessment of laboratory variables will be tabulated by time point for each clinical laboratory analyte for the Safety Population by treatment arm and dose level (frequency tables). Additionally, for each laboratory parameter, shifts in assessments from baseline to all

post-administration time points will be presented for the recommended dose groups of each treatment arm (shift tables).

Grades for a clinical laboratory analyte will be derived according to NCI CTCAE, version 4.0 and used to present additional frequency and shift tables based on NCI CTCAE grades.

The assessment of categorical urinalysis variables will be tabulated by time point for each urine parameter for the Safety Population by part and dose level (frequency tables). Additionally, for each of these urine parameters, shifts in assessments from baseline to all post-administration time points will be presented for the recommended dose groups of each treatment arm (shift tables).

Laboratory values that are outside the reference range will also be flagged in the data listings, along with corresponding reference ranges.

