10.3 Clinical Laboratory Evaluations

Safety laboratory data (hematology, serum chemistry, endocrinology, coagulation, urinalysis) will be analyzed by the respective local laboratories of each involved site.

The analysis of safety laboratory parameters will be presented separated into blood parameters (hematology, serum chemistry, endocrinology, coagulation) and urine parameters (urinalysis). All data will be listed.

The blood parameters will be transformed to SI values based on SI units to make laboratory parameters comparable between different local laboratories. The relevant reference ranges supplied by each laboratory will also be transformed to SI reference ranges for each laboratory.

Descriptive summaries of actual (absolute) values and changes from baseline values will be presented for all blood parameters.

Creatinine clearance will be calculated according to the Cockcroft-Gault formula and will be included in descriptive summaries of actual (absolute) values and changes from baseline.

Each abnormal value will be flagged to show whether it is a value below or above the reference range. For the assessment of laboratory variables, 5 categories will be used that take into account

the investigator's assessment of clinical relevance: 'clinically relevant, above', 'non-clinically relevant, above', 'within', 'non-clinically relevant, below', 'clinically relevant, below'.

The assessment of laboratory variables will be tabulated by time point for each clinical laboratory analyte (frequency tables).

If NCI-CTCAE grades are available for a clinical laboratory analyte, these will be derived according to NCI-CTCAE version 4.0 and used to present additional frequency based on NCI-CTCAE grades.

For hematology parameters, shifts in assessments from baseline to worst-post baseline will be presented based on classifications relative to the laboratory reference ranges (low/normal/high) for hematology parameters where NCI-CTCAE grades are not defined. If a subject experiences both "Low" and "High" assessments in the course of the trial, the worst post-baseline will be defined as "Low and High".

If NCI-CTCAE grades are available for a hematology parameter, frequency, shift and summary tables based on grades will be created as follows:

- Incidence of subjects with worst post-baseline grade. Each subject will be counted only for the worst grade
- Shift tables to compare baseline to the worst post-baseline value using CTCAE grades

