- Summary of time to onset to worst post-baseline grade (defined as the time from treatment start to first occurrence of worst post-baseline grade): this table will present summary statistics over all grades, but only patients with a worst post-baseline grade will be included.

A separate listing will be prepared to list the time course of a laboratory parameter for a subject with any abnormal, clinically significant laboratory value (for all laboratory values irrespectively of whether NCI-CTCAE grades are available).

The investigator's assessment of categorical urinalysis variables ('normal', 'abnormal, not clinically significant', 'abnormal clinically significant') will be tabulated by time point for each urine parameter (frequency tables).

Additionally, for each of these urine parameters, shifts in assessments from baseline to Cycle 2 Day 1 and to EOS will be presented for combined data.

For all shift tables, baseline percentage will be based on the number of patients in the analysis set (N). Percentage for worst post-baseline value will be based on Baseline n for the baseline category the percentage refers to.

Laboratory values that are outside the reference range will also be flagged in the data listings, along with corresponding reference ranges.

Results of unscheduled laboratory evaluations, laboratory data of the emergency laboratory, results of urine microscopy (if available), results of the pregnancy test and screening serology results will only be included in listings.

In general, laboratory summaries except for the tables analyzing the hematology parameters (worst post-baseline assessments/grades) as described above will only include time points of Cycle 1+2 and EOS visit. For the tables analyzing the hematological parameters, all available time points will be included when deriving worst assessment/worst grade.

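### SAP 10.3 describes no shift or worst-grade table for serum chemistry, coagulation or endocrinology, and in general limits their summaries to Cycles 1–2 and EOS

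*SAP*

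**What the plan says.** **Protocol 15.7.3** counts hematology, serum chemistry, endocrinology and coagulation as blood parameters. For the recommended dose groups it plans, "for each laboratory parameter, shifts in assessments from baseline to all" post-administration time points. It adds that CTCAE grades will be "used to present additional frequency and shift tables based on NCI CTCAE grades".

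**SAP 10.3** carries over the grade sentence without the shift tables: grades are "used to present additional frequency based on NCI-CTCAE grades". It then turns to one class of blood parameter: "For hematology parameters, shifts in assessments from baseline to worst-post baseline will be presented". The worst-grade incidence, grade shift and time-to-worst-grade tables are likewise set out for hematology. Urinalysis has shifts to Cycle 2 Day 1 and EOS. No shift table is described for serum chemistry, coagulation or endocrinology.

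On time points, the closing paragraph of 10.3 exempts the hematology worst-value tables, for which "all available time points will be included when deriving worst assessment/worst grade". The remaining laboratory summaries are in general held to the window: "worst post-baseline assessments/grades) as described above will only include time points of Cycle 1+2 and EOS visit".

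**SAP 7.1** makes all cycles the default for tables unless stated otherwise, so 10.3 is the operative exception. **SAP 4.3** plans a long-term follow-up analysis that re-runs everything in the SAP.

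**SAP 10.4 and 10.5** have a related wording problem. Vital-sign summaries are said to cover every time point, and QTc category shifts every visit after baseline. Each section then closes with the same general limit to Cycles 1–2 and EOS. SAP 10.5 also summarises QTc under both corrections and later places the Fridericia values in listings only.

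**The concern.** The safety profile is a primary objective, and laboratory change, with serum chemistry named, is secondary endpoint 7. Treatment may continue for up to three years, and Protocol Tables 1 and 2 mark serum chemistry at every Cycle 3+ treatment visit.

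Under 10.3 as written, a liver, renal or electrolyte change that begins in Cycle 3 or later and has resolved by EOS would appear in no chemistry summary that the section describes. The long-term safety re-run would not correct this. Cycles 1–2 are already complete at the primary analysis (SAP 4.2), so the re-run chemistry tables would gain essentially only further EOS values. The same SAP extends by-visit response, pharmacodynamic and other summaries to Cycle 6 and Cycle 12 (SAP 9.2, 9.3, 9.5), so safety chemistry is cut off earlier than these.

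**Working it through.** The plan states no figure on this point, so the check compares texts and counts scheduled samples.

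**1. Tables described for each parameter class**

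| Class | Protocol 15.7.3 | SAP 10.3 text |
|---|---|---|
| Hematology | shifts to all post-administration time points; grade shifts | baseline-to-worst shifts, by grade or by low/normal/high, over all time points |
| Serum chemistry | same | descriptive and frequency tables only; Cycles 1–2 and EOS |
| Coagulation, endocrinology | same | as for chemistry |
| Urinalysis | shifts to all post-administration time points | shifts to Cycle 2 Day 1 and EOS |

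Urinalysis loses no scheduled sample, because its only scheduled post-baseline samples are Cycle 2 Day 1 and EOS. Coagulation and endocrinology have no Cycle 3+ treatment samples, but both are taken at Follow-up Visit 1, which lies outside the window.

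**2. Analytes.** Protocol Table 11 lists 22 serum chemistry items. Removing β2-microglobulin (screening only) gives 22 − 1 = 21. Removing optional bicarbonate as well gives 20. SAP 10.3 describes a shift table for none of them.

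**3. Scheduled chemistry samples outside the window.** Protocol Table 2 has 10 chemistry visits in Cycles 1–2 (Days 1, 2, 4, 8, 15, 22, 29, 36, 43, 50). Dose levels 8c/8d/8e have 4 visits in Cycle 3 and then 2 per cycle. Dose levels 7c/7d/7e stay weekly, with 4 per cycle. The documents give no expected treatment duration, so the durations below are assumptions. Share = late visits / (10 + late visits).

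| Cycles treated | 8c/8d/8e | 7c/7d/7e |
|---|---|---|
| 3 | 4/14 = 29% | 4/14 = 29% |
| 6 | 10/20 = 50% | 16/26 = 62% |
| 12 | 22/32 = 69% | 40/50 = 80% |

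The 10 early visits include the pre-dose Day 1 sample, which is the baseline under SAP 7.1. Leaving it out raises the six-cycle shares slightly, to 10/19 = 53% and 16/25 = 64%.

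**4. ECG.** In Part D, Protocol 10.1.13 schedules ECGs on Day 1 of Cycles 3, 6, 9 and so on: four by Cycle 12, all outside the window. The ECG at treatment discontinuation is also outside if it falls after Cycle 2 and is not the EOS one.

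**The case against.** The strongest reply has four parts.

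**The tables may exist.** The SAP's list of tables is redacted, and the grade-frequency sentence in 10.3 reads as though words were dropped. A reader might infer that the sponsor decided to remove chemistry shifts. The documents do not support that; they show only that 10.3 does not describe them. Nor is the lack of a deviation note in the SAP a breach, because Protocol 15.13 places such notes in the final study report.

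**The window has a rationale.** The primary analysis is triggered at Cycle 3 Day 1 or end-of-study assessments, so Cycles 1–2 and EOS are what it covers for all subjects. Recommended-dose groups may hold as few as 9, and Cycle 3+ is offered to those with at least stable disease. Late by-visit cells would therefore be sparse and selected. This is a fair argument against by-visit tables. It does not apply to a worst-post-baseline table, and it does not explain the follow-up re-run.

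**Little escapes.** A reader might infer that late chemistry data are lost. They are not. All values are listed, and a separate listing will "list the time course of a laboratory parameter for a subject with any abnormal, clinically significant laboratory value". Clinically significant values are AEs by definition (Protocol 11.3.1), AE tables cover all cycles, and a grade 4 value not reported as an AE needs a documented rationale (Protocol 11.3.4). Endpoint 7 concerns absolute change and clinically relevant values, not shifts. All this limits the impact, but the chemistry summaries for endpoint 7 are still subject to the window.

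**Late panels may vary.** Protocol 10.1.13 ties Cycle 3+ laboratory work to local practice, with a stated minimum. Completeness of all 21 analytes at each late visit is not assured.

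On ECG and vital signs, the closing limits are general rules that may yield to the more specific sentences. That leaves the programmed window unclear rather than wrong.

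**Conclusion.** The point stands at moderate weight. On the text of SAP 10.3, the planned laboratory tables fall short of Protocol 15.7.3 for serum chemistry, coagulation and endocrinology. Followed as written, 10.3 leaves a late chemistry change that resolves before EOS out of every chemistry summary it describes, in both the primary and the follow-up analysis. A change still present at EOS would appear.

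This rests on the visible 10.3 text, because the table list is redacted, and on reading its general limit as the working rule. The gap is in summaries, not in data. What escapes both the chemistry summaries and the AE tables is limited to changes that are late, transient and not judged clinically significant.

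The shares in the working might be read as the proportion of safety information lost. They cannot be: they are schedule counts under assumed durations. The protocol's shift tables also cover recommended-dose groups only, so at most one of the two schedules bears on that promise within a part.

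The vital-sign and QTc inconsistencies are wording matters of lesser weight. The Part D ECGs are the reason to settle the QTc sentences explicitly.

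**What to change.** **SAP 10.3**
- Extend the hematology tables (worst post-baseline CTCAE grade, and baseline-to-worst shift) to serum chemistry over all available visits, using low/normal/high where no grade exists.
- Add baseline-to-worst shifts for coagulation and endocrinology, including follow-up visits.
- State whether all available time points include unscheduled values. The section otherwise sends "Results of unscheduled laboratory evaluations, laboratory data of the emergency laboratory" and some other results to listings only.
- If baseline-to-worst replaces the protocol's shifts to all post-administration time points, record the change and its reason in the study report, as Protocol 15.13 asks.

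**SAP 10.5**
- Reconcile the QTc shift sentence with the closing window, so that scheduled Part D ECGs from Cycle 3 onward enter the QTc category, change and shift tables.
- Decide whether the Fridericia values are summarised or only listed, and make the two sentences agree.

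**SAP 10.4**
- Reconcile the two time-point sentences. Protocol 15.7.4 says all time points.

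**Cost:** a few more tables, mostly from the existing hematology programs, and no new data. If late by-visit vital-sign and ECG summaries are kept, their cells will be sparse.

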10.4 Vital Signs and Body Weight

Descriptive summaries of actual values and changes from baseline will be calculated for vital signs (systolic blood pressure [SBP], diastolic blood pressure [DBP], body temperature, heart rate [HR], and respiratory rate [RR]) and body weight and BMI. These summaries will be presented for all time points.

Each abnormal value will be flagged to show whether it is a value below or above the normal limit. The normal limits are detailed in the appendix of the study protocol (section 18.2 of the study protocol).

In general, vital signs summaries will only include time points of Cycle 1+2 and EOS visit.

10.5 Electrocardiograms

The summary ECG assessment (categories: <normal; abnormal clinically significant; abnormal not clinically significant>) will be tabulated by visit.

Each abnormal PR, QRS, and RR interval value will be flagged to show whether it is a value below or above the normal limit. The normal limits are detailed in the appendix of the study protocol (section 18.2 of the study protocol).

Descriptive summaries of actual values and changes from baseline will be presented by visit for ECG measures of RR interval, PR interval, QRS interval, QT interval, QTc interval (both correction methods), and HR (Heart rate).

The Bazett's Correction (QT_{c_b}) and Fridericia's Correction (QT_{c_f}) for the QTc interval will be derived as follows:

$$\text{Bazett's Correction (QT}_{c_b}\text{)} \quad QT_{c_b} = \frac{QT_{msec}}{\sqrt{RR}}$$

$$\text{Fridericia's Correction (QT}_{c_f}\text{)} \quad QT_{c_f} = \frac{QT_{msec}}{\sqrt[3]{RR}}$$

where: RR = Relative Rate = 60 / HR

HR = Heart Rate obtained from the ECG.

Also, the number and percent of subjects with QTc values (Bazett's correction) above the normal limit (441-480 ms, 481-500 ms, or > 500 ms) and the number and percent of subjects who experienced a change > 30 ms or a change > 60 ms from baseline will be presented by visit.

Moreover, shifts in QTc category (Bazett's correction) from baseline to all post-baseline visits will be presented for combined data, based on the following categories (normal, 441-480 ms, 481-500 ms, or > 500 ms).

QTcF interval will only be presented in listings (along with the QTcB interval).

In general, ECG summaries will only include time points of Cycle 1+2 and EOS visit.

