### **15.7.5 Electrocardiograms**

The summary ECG assessment (categories: <normal; abnormal clinically significant; abnormal not clinically significant>) will be tabulated by time point for the Safety Population by treatment arm and dose level.

Each abnormal PR, QRS, and RR interval value will be flagged to show whether it is a value below or above the normal limit. The normal limits are detailed in Appendix 18.2).

Summary statistics for all time points will be displayed for QT and QTc correction methods, side-by-side, and by treatment arm and dose level. The Bazett's corrections method for QTc will be applied as follows:

Bazett's Correction (QTc_b) 
$$QTc_b = \frac{QT_{msec}}{\sqrt{RR}}$$

where: Relative Rate: RR = 60 / heart rate (HR)

Also, the number and percent of subjects in each treatment arm and dose level with QTc values above the normal limit (441-480 ms, 481-500 ms, or > 500 ms) and the number and percent of subjects in each treatment arm and dose level who experienced a change > 30 ms or a change > 60 ms will be presented by time point.

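### SAP 10.5 contradicts itself on whether QTcF is tabulated, and no QTc category, change or shift table names any method but Bazett

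*SAP*

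**What the plan says.** SAP 10.5 Electrocardiograms lists the ECG measures to be summarised descriptively at each visit, as observed values and as changes from baseline. Among them is "QTc interval (both correction methods". The section then gives a Bazett and a Fridericia formula, both using the same RR ("where: RR = Relative Rate = 60 / HR").

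The threshold tables follow. One counts subjects with "QTc values (Bazett's correction) above the normal limit (441-480 ms, 481-500 ms, or > 500 ms". The same sentence adds counts of subjects whose change exceeds 30 ms or 60 ms, without naming a method for those counts. A further table covers "shifts in QTc category (Bazett's correction) from baseline to all post-baseline visits will be presented for combined data". The section then says: "QTcF interval will only be presented in listings".

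Protocol 15.7.5 Electrocardiograms says: "Summary statistics for all time points will be displayed for QT and QTc correction methods, side-by-side". It then defines one correction only, Bazett.

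**The concern.** There are two difficulties. First, a programmer cannot both summarise QTcF by visit and confine it to listings. The planned-table list is redacted in the public SAP, so it cannot show which sentence was implemented.

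Second, if the listings-only sentence governs, QTcB is the only heart-rate-corrected QT in any table. If the other sentence governs, QTcF gains by-visit summaries, but the tables that count subjects past a limit still name only Bazett. QTcB depends more steeply on heart rate than QTcF does. A subject can therefore cross a category limit or the 30 ms change cut-off on QTcB while QTcF stays where it was. With cohorts of three to six subjects and recommended-dose groups of at least nine, one or two such subjects visibly change a percentage.

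**Working it through.** The plan attaches no sample size, test or stated figure to this display, so there is nothing to reproduce. The check uses the SAP's formulas and limits.

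**Inputs**
- Bazett: QTcB = QT / RR^(1/2). Fridericia: QTcF = QT / RR^(1/3). RR = 60/HR (SAP 10.5).
- Category limits 440, 480 and 500 ms; change cut-offs 30 and 60 ms (SAP 10.5).
- Normal pulse 60 to 100 bpm (Protocol Appendix 18.2, Table 12). The normal RR interval in Table 13, 600 to 1000 ms, is the same range: 60,000/600 = 100 and 60,000/1000 = 60 bpm.
- Heart rates and QTcF values within these ranges are assumed for illustration.

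**Ratio of the two corrections**

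QTcB/QTcF = RR^(1/3) / RR^(1/2) = RR^(-1/6) = (HR/60)^(1/6).

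A subject is above a limit L by Bazett but not by Fridericia when QTcF lies between L divided by the ratio and L.

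| HR (bpm) | Ratio | QTcF counted above 440 ms by Bazett | QTcF counted above 480 ms by Bazett |
|---|---|---|---|
| 60 | 1.000 | none | none |
| 80 | 1.049 | 419.4 to 440 | 457.5 to 480 |
| 90 | 1.070 | 411.2 to 440 | 448.6 to 480 |
| 100 | 1.089 | 404.1 to 440 | 440.8 to 480 |

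Below 60 bpm the direction reverses. At 50 bpm the ratio is 0.970, so a QTcF of 440 to 453.6 ms is tabulated as normal by Bazett.

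**A single recording.** QT 360 ms at 100 bpm (RR 0.6) gives QTcB = 360/0.6^(1/2) = 464.8 ms, in the 441-480 category. QTcF = 360/0.6^(1/3) = 426.8 ms, which is normal.

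**Change from baseline with QTcF constant at 410 ms**
- HR 60 to 100: 410 × (1.0889 − 1.0000) = 36.4 ms. This passes the 30 ms cut-off and moves QTcB from 410 to 446.4 ms, out of the normal category.
- HR 70 to 100: 410 × (1.0889 − 1.0260) = 25.8 ms. This does not pass the 30 ms cut-off.

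**The case against.** The strongest reply is that the only outright defect is one sentence against another, and that deleting either would make the section consistent. The category and shift tables are labelled Bazett without ambiguity, in line with the only correction the protocol defines. ECG findings are not among the listed primary or secondary endpoints. No formal test or stated escalation rule uses these tables. All of that stands, and it keeps the point a minor one. It does not remove the contradiction, and it does not explain why a QTcF that is already derived should be left out of the tables where the choice of correction matters most.

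Several stronger readings are tempting, but the documents do not support them:
- **That QT conclusions rest on Bazett alone.** Uncorrected QT, RR and heart rate are also summarised by visit, the investigator's overall ECG assessment is tabulated, and QTcF is listed per subject beside QTcB. A careful reader can see whether a QTcB change came with a heart-rate change.
- **That the protocol requires Fridericia.** Its side-by-side wording could mean uncorrected QT beside QTcB, since no second formula is given. It does not settle the conflict.
- **That the gap is typically two categories.** A move from normal to 481-500 ms needs a ratio above 480/440 = 1.091, hence a heart rate above about 101 bpm, just outside the normal pulse range. A two-category gap inside that range arises only by skipping the narrow 481-500 band: at 100 bpm a QTcF of 459.2 to 480 ms reads as above 500 ms by Bazett.
- **That holding raw QT fixed while heart rate rises isolates a Bazett artefact.** QTcF rises too: at QT 360 ms it goes from 412.1 ms at 90 bpm to 426.8 ms at 100 bpm. The comparison has to hold QTcF constant, as above.
- **That infusion-day heart-rate changes drive the effect.** No scheduled ECG is described as taken during an infusion. Several of those for weekly subjects (Days 8, 22 and 50) are listed before dosing, and Protocol 11.3.5 has recordings made after five minutes supine.

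**Conclusion.** The point holds as an internal contradiction with a modest reporting consequence. SAP 10.5 cannot be programmed as written. Under either reading its category and shift tables use Bazett only, and its change counts name no other method. Within the protocol's normal pulse range Bazett is never below Fridericia and is up to 8.9% higher. That is enough to count a QTcF of about 404 to 440 ms as above 440 ms at 100 bpm, or to produce a change above 30 ms from heart rate alone when it rises from 60 to 100 bpm. A rise from 70 to 100 bpm falls short of that cut-off at a QTcF of 410 ms. Slow heart rates can hide prolongation instead.

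The arithmetic follows from the SAP's formulas; the heart rates and QTcF values are assumptions. How many subjects would be classed differently cannot be computed without a QT and heart-rate distribution. This is a cheap improvement to a descriptive safety display and does not threaten a primary conclusion.

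**What to change.** Delete the listings-only sentence in SAP 10.5, so that QTcF appears in the by-visit summaries the section already promises. Show QTcF beside QTcB in the category table (441-480, 481-500 and above 500 ms), the counts of changes above 30 and 60 ms, and the shift table. State the correction method for the change counts explicitly. QTcF is already derived, so no new data are needed and no clinical rule changes. The cost is a few duplicate descriptive tables. At the least, the two conflicting sentences must be reconciled.
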